7.4 Safety Assessments

7.4.1 Adverse Events

Assessment of adverse events will include type, incidence, severity (graded by the National Cancer Institute [NCI] Common Terminology Criteria for Adverse Events [CTCAE, Version 4.03]), timing, seriousness, and relatedness to study treatment.

Signs and symptoms of the patient's cancer diagnosis and/or comorbidities present at baseline will be recorded in the CRF as adverse events. Treatment-emergent adverse events will be reported separately from signs and symptoms of the patient's cancer diagnosis and/or comorbidities that are present at Day 1. The actual date of onset should be recorded in all cases. Ongoing AEs that change in attribution or severity should have the date of change entered as the "end date" and a new AE record should be opened with the changed details.

7.4.2 Physical Examination and Vital Signs

A physical examination including all major body systems is mandated at Screening and End of Treatment Visits only. During study treatment, symptom directed physical examinations will be performed.

Vital signs to be assessed include weight, body temperature, blood pressure, and pulse rate. Height will be recorded at screening only. On days when both vital signs and PK sampling are scheduled, the vital signs should be assessed prior to blood sampling.

Clinically significant findings noted during screening will be reflected on the medical history CRF, while those noted during study treatment will be collected on the AE CRFs.

7.4.3 Laboratory Safety Assessments

Laboratory safety assessments for which data will be collected in this study will include hematology, coagulation, and chemistry parameters presented in Table 9.

Laboratory tests will be drawn at the time points described in the Schedule of Assessment table and analyzed at local laboratories. Additional laboratory tests may be performed per standard of care, at the investigator's discretion for the purpose of planning treatment administration, dose modification, following adverse events, or as clinically indicated.

Table 9: Laboratory Safety Parameters

Hematology Panel	Blood Chemistry Panel
Hemoglobin	Aspartate aminotransferase (AST)
Platelet count	Alanine aminotransferase (ALT)
White blood cell count (WBC)	Alkaline phosphatase
Neutrophil count	Total bilirubin
Lymphocyte count	Creatinine
Eosinophil count	Uric acid
Basophil count	Albumin
Monocyte count	Sodium
	Potassium
Coagulation	Chloride
International normalized ration (INR)	Total calcium
Partial thromboplastin time (PTT)	Phosphate
	Magnesium

Pregnancy Testing: For patients of childbearing potential, a serum or urine pregnancy test will be performed at screening. Pregnancy tests will also be done whenever pregnancy is suspected during the study. Additional pregnancy testing may be necessary if required by local practices or regulations.

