1.2.3 Clinical Data

MGCD265 has been evaluated using various oral formulations and regimens in Phase 1 and 1/2 clinical trials in over 370 patients with advanced malignancies. The safety profile of single agent administration and combinations of MGCD265 and docetaxel or

erlotinib has been evaluated. Details on clinical trial experience are presented in the [MGCD265 Investigator's Brochure \(IB\)](#).

When MGCD265 was administered as a single agent, the most common related treatment-emergent adverse events (TEAEs) were diarrhea (62%), nausea (39%), fatigue (31%), vomiting (26%), aspartate aminotransferase increased (25%), and alanine aminotransferase increased (20%). Grade 3 related TEAEs reported in more than one patient included diarrhea (8%), fatigue (5%), aspartate aminotransferase increased, alanine aminotransferase increased, lipase increased, nausea, and vomiting (2% each), and abdominal pain, anemia, blood alkaline phosphatase increased, blood phosphorus decreased, dehydration, hypertension, and hypokalemia (1% each); Grade 4 related TEAEs included lipase increased (1%) and amylase increased and lymphocyte count decreased (< 1%).

The MGCD265 formulation and regimen to be used at the initiation of the current study is non-aqueous suspension capsules (MGCD265 free base suspended in Miglyol[®] in soft gelatin capsules and referred to as soft gel capsules), administered twice daily (BID) in a continuous regimen (delivered in 21-day cycles). In the Phase 1 study, MGCD265 systemic exposure increased with increasing dose from 600 to 1050 mg BID, with a less than dose proportional manner between 1050 and 1200 mg BID. The maximum tolerated dose with the soft gel capsules was established at 1050 mg BID. Following single dose administration of 1050 mg BID soft gel capsules, MGCD265 was absorbed, with maximum concentration (C_{max}) occurring at a median time of 8 hours (4-12 hours range) after dosing. The mean elimination half-life was 36.7 ± 13.6 hours (mean \pm SD). At steady state, the geometric mean $C_{max,ss}$, $C_{ave,ss}$ and $AUC_{0-12,ss}$ values were 510 ng/mL, 464 ng/mL, and 5572 ng•h/mL, respectively. Drug accumulation was observed after multiple dose administration, whereby C_{max} and AUC_{0-12} were 3.9-fold and 5.2-fold higher, respectively, than single dose administration of 1050 mg soft gel capsules. Mean peak to trough ratio at steady state was 1.18.

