5.2.2 Adverse Event Management Guidelines

Management of toxicities \geq Grade 3 and considered to be treatment-related should include treatment interruption until resolution of toxicity to \leq Grade 1 or to baseline

value. If the toxicity may be adequately managed by routine supportive care (such as anti-emetics, anti-diarrheals, or electrolyte supplementation), treatment may be resumed at the same dose; if not, treatment may be resumed at a reduced dose as described in Table 7. Recurrence of the toxicity may be managed similarly. If treatment is interrupted for more than 3 weeks, permanent discontinuation from study treatment should be considered.

Table 7: Dose Modifications – Treatment-Related Toxicities

Toxicity	Treatment Delay	Dose Modification
< Grade 3	May be implemented based on Investigator and patient discretion	
Grade 3 or 4, manageable with routine supportive care	Hold until \leq Grade 1 or return to baseline	Not required
Grade 3 or 4, not manageable with routine supportive care	Hold until \leq Grade 1 or return to baseline	Resume at a dose level one or more levels below that inducing the toxicity

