8.2.1 Laboratory Abnormalities

An abnormal laboratory test results should be reported as an AE in the CRF only if it is associated with one or more of the following:

- Clinical symptoms;
- Requires additional tests (beyond repeats), treatment or intervention;
- Results in change in study treatment dosing;
- Requires discontinuation from study treatment; and/or
- Considered by the investigator or Sponsor to be an AE.

Hy's Law

Hepatic function abnormality defined by an increase in AST and/or ALT to $\geq 3 \times$ ULN concurrent with an increase in total bilirubin to $\geq 2 \times$ ULN but without increase in alkaline phosphatase (i.e., alkaline phosphatase $< 2 \times$ ULN) meets the criteria for Hy's Law and raises the concern for drug-induced liver injury when no other cause of the abnormal laboratory results is identified. Follow-up investigations and inquiries will be initiated promptly by the investigational site to determine whether the findings are reproducible and/or whether there is objective evidence that clearly supports causation by a disease (e.g., cholelithiasis and bile duct obstruction with distended gallbladder) or an agent other than the investigational product.

Cases meeting Hy's Law should be reported as SAEs. Study drug should be permanently discontinued for a Hy's Law case.

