9.5.3 Clinical and Laboratory Assessments

Clinical and laboratory assessments include clinical laboratory tests (hematology, coagulation, and chemistry), vital signs, and 12-lead ECGs.

Clinical laboratory results will be listed by patient and, as appropriate, summarized descriptively, which will include a display of change from baseline. Selected parameters will be presented in shift tables of baseline against worst grade test result. Laboratory values outside of the normal ranges will be identified. Laboratory values that meet Grade 3 or 4 criteria according to NCI CTCAE v.4.03 will be listed and summarized.

ECG assessments will be evaluated for change of QTc from baseline as an exposure: response analysis. The investigator's interpretation of QTc will be used in the clinical management of patients. The study analysis will use Fridericia's formula applied programmatically to the ECG data collected in CRFs.

Vital signs and ECG measurements will be listed for each patient at each visit. Descriptive statistics of observed values and changes from baseline will be summarized by treatment group.

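### Lipase and amylase, both reported as drug-related Grade 4 events, are in no scheduled laboratory panel, so the incidence of asymptomatic rises is likely to be under-ascertained

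*Combined protocol and SAP*

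**What the plan says.** **Known toxicity (section 1.2.3).** For single-agent use, the drug-related Grade 3 events seen in more than one patient include "lipase increased, nausea, and vomiting (2% each"). At Grade 4 the text reads "Grade 4 related TEAEs included lipase increased (1%) and amylase increased and lymphocyte count decreased (< 1" percent).

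**What is measured (section 7.4.3).** "Laboratory safety assessments for which data will be collected in this study will include hematology, coagulation, and chemistry parameters presented in Table 9". The chemistry column of Table 9 has 13 entries: AST, ALT, alkaline phosphatase, total bilirubin, creatinine, uric acid, albumin, sodium, potassium, chloride, calcium, phosphate and magnesium. Table 2 schedules serum chemistry at screening, on Days 1 and 15 of Cycles 1 and 2, on Day 1 of later cycles and at End of Treatment. Lipase and amylase appear nowhere outside section 1.2.3.

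**What is optional.** Section 7.4.3 adds: "Additional laboratory tests may be performed per standard of care, at the investigator's discretion". The introduction to Table 2 also asks for unplanned assessments where clinically indicated.

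**What happens to a result.** Under section 5.2.2, management of toxicities of Grade 3 or higher "considered to be treatment-related should include treatment interruption until resolution of toxicity to" Grade 1 or lower, or to baseline. Under section 8.2.1 an abnormal result "should be reported as an AE in the CRF only if it is associated with" at least one of five conditions. These include a change in dosing and a judgment by the investigator or the Sponsor that it is an AE. Section 9.5.3 states: "Laboratory values that meet Grade 3 or 4 criteria according to NCI CTCAE v.4.03 will be listed and summarized".

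**The concern.** Section 2.2.2 makes the type, incidence and severity of laboratory abnormalities part of a secondary endpoint. The incidence of a laboratory toxicity can be estimated only if the analyte is measured in all patients on a common schedule. A rise in lipase or amylase without symptoms gives the site little cue to order the test, sites will differ in how often they do so, and values obtained that way have no clear denominator.

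Two things are at stake. The Grade 3/4 laboratory tables would be incomplete for two toxicities that the sponsor already attributes to the drug. Also, sections 3 and 9.1 allow enrolment to be expanded partly to enlarge the safety database for a possible accelerated approval application. If that happens, a low observed rate of lipase rises could not be told apart from a low rate of testing.

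**Working it through.** The plan states no figure on this point, so the main check is a side-by-side reading.

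**Step 1. Match each laboratory-based Grade 3 or 4 term in section 1.2.3 to Table 9.**

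| Term | Grade 3 | Grade 4 | Analyte in Table 9 |
|---|---|---|---|
| AST increased | 2% | not named | yes |
| ALT increased | 2% | not named | yes |
| Lipase increased | 2% | 1% | **no** |
| Anemia | 1% | not named | yes (hemoglobin) |
| Alkaline phosphatase increased | 1% | not named | yes |
| Phosphorus decreased | 1% | not named | yes (phosphate) |
| Hypokalemia | 1% | not named | yes (potassium) |
| Amylase increased | not named | < 1% | **no** |
| Lymphocyte count decreased | not named | < 1% | yes |

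Seven of the nine terms are covered. The two that are not are two of the three terms named at Grade 4, and lipase has the highest rate stated at that grade.

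**Step 2. Follow a site that does exactly what is scheduled.** Each chemistry draw in Table 2 yields the Table 9 analytes. An asymptomatic patient with a high lipase has no lipase value, so nothing brings section 5.2.2 into play, nothing reaches section 8.2.1, and nothing enters the section 9.5.3 listing. If the test is ordered for another reason, the result can move through all three.

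**Step 3. Scale.** Assumptions: the single-agent rates in section 1.2.3 carry over to this trial, and the Grade 3 and Grade 4 patients are different people. Formula: expected cases = n × p.

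- Combined Grade 3-4 lipase rate: 2% + 1% = 3%. As printed, 2% can mean 1.5% to 2.5% and 1% can mean 0.5% to 1.5%, so the sum runs from 2% to 4%.
- Maximum enrolment, n = 4 × 45 + 2 × 55 = 290 (agrees with section 9.1): 290 × 0.03 = 8.7; range 290 × 0.02 = 5.8 to 290 × 0.04 = 11.6.
- No expansion, n = 4 × 45 = 180: 180 × 0.03 = 5.4; range 3.6 to 7.2.
- One full arm, n = 45: 45 × 0.03 = 1.35 expected; chance of at least one = 1 − 0.97^45 = 0.75.
- Grade 4 lipase alone: 290 × 0.01 = 2.9; chance of at least one in a 45-patient arm = 1 − 0.99^45 = 0.36.
- Grade 4 amylase is given only as below 1%, so fewer than 2.9 of 290.

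These counts cover all Grade 3-4 lipase events, with or without symptoms. Section 1.2.3 does not give the asymptomatic share, so the number that would be missed cannot be calculated.

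**The case against.** The strongest case on the other side is that the protocol leaves a route open at every step. Tests may be added at the investigator's discretion, and the introduction to Table 2 calls for them when clinically indicated. Section 5.2.2 applies to any related toxicity of Grade 3 or higher once it is known. A value that changes dosing is reportable under section 8.2.1. Section 7.4.3 says what the laboratory data will include, which is not exclusive wording, and section 9.5.3 does not limit its listing to Table 9.

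All of this stands, and it rules out several stronger readings that a reader might infer:

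- *That these rises would go undetected, unacted on and uncounted, or that the Grade 3-4 rule cannot operate for them.* The routes above contradict this. What is missing is a scheduled test.
- *That this is the drug's most severe known toxicity.* Section 1.2.3 reports graded enzyme rises, and its Grade 4 list is introduced as what was included, so it may not be complete. The text supports only that lipase has the highest stated Grade 4 rate.
- *That the observed rate will fall far below Phase 1 because of non-measurement.* The Phase 1 laboratory schedule is not in the documents, so the size of any shortfall cannot be predicted.
- *That about 9 cases would be missed.* The 8.7 counts all events, at the enrolment ceiling.

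The carry-over of rates is also open to question. The earlier experience, described as "Phase 1 and 1/2 clinical trials in over 370 patients with advanced malignancies", spans several formulations and regimens, and no single-agent denominator is given. Section 1.2.3 also reports a trend to fewer and milder adverse events with the tablet formulation that newly enrolled patients now receive. Enrolment may stop well short of 290, since section 9.1 expects 28 patients per arm if the true response rate is 20%.

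None of this replaces scheduled measurement. Discretionary testing can find individual cases, but it does not give an incidence.

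**Conclusion.** The point holds as a gap in ascertainment. Two laboratory toxicities that the protocol itself attributes to the drug have no scheduled test, while the other seven laboratory-based Grade 3/4 terms do, and no reason is given. Detection of asymptomatic rises, and any action on them, depends on discretionary or clinically indicated testing. The section 9.5.3 summary would not capture them systematically, so their incidence is likely to be under-ascertained.

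Absence from Table 9 and from the schedule is certain. The size is indicative only: about 8.7 Grade 3-4 lipase cases of any kind in at most 290 patients (5.8 to 11.6), or 5.4 in 180 (3.6 to 7.2). Both figures rest on the carry-over of the single-agent rates and on distinct Grade 3 and Grade 4 patients. The number of asymptomatic cases missed is unknown. The point does not affect the primary endpoint. It should be fixed because the remedy is cheap and values that were never measured cannot be recovered later.

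**What to change.** Reconcile section 1.2.3 with Table 9 in one of two ways.

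1. Add lipase and amylase to the Table 9 chemistry panel, measured on the serum chemistry draws already in Table 2. Carry the values into the CRF laboratory page and the Grade 3/4 listing and summary in section 9.5.3.
2. Keep Table 9 as it is, give the reason for leaving the two enzymes out, and state in the safety reporting that their rates are not systematically ascertained.

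No dose, hold or other clinical rule is proposed; section 5.2.2 is left as written.

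**Cost.** The first option needs a protocol amendment, CRF entries for the two analytes and two more local assays per draw, with no extra visit or procedure. Its downside is that some treatment interruptions would follow under the existing rule for asymptomatic rises that would otherwise go unseen. The second option costs only text, but leaves the incidence unknown.

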7.4.4 Electrocardiogram (ECG)

Single and triplicate ECGs are to be performed as outlined in the Schedule of Assessments. It is preferable that the machine used has a capacity to calculate the standard intervals automatically. Assessments reported by automated read as prolongation of QTc > 480 msec should be over-read by a cardiologist to ensure accuracy of interpretation.

7.5 Laboratory Studies

Laboratory studies for which blood will be collected include evaluation of PK, PD and ctDNA. The schedules for sample collection are outlined in Table 2 and Table 3. Blood samples will be collected using an in-dwelling catheter or venipuncture into specified

vacutainer tubes. Full details on sample processing, storage and shipment are presented in the Study Laboratory Manual.

7.5.1 Pharmacokinetic Evaluation

The PK of MGCD265 will be determined using plasma samples collected at specified time points prior to and following study treatment dosing. Every effort will be made to collect these PK samples at the exact nominal times relative to dosing. A variation window is allowed for each time point as outlined in Table 3. The actual time of drug administration and each PK sample collection will be recorded in the patient's source document and the CRF.

At each PK time point, blood samples will be collected into 6-mL K2EDTA tubes. For PK analysis, a total of approximately 48 mL of blood will be collected from each patient. Analysis of plasma samples for MGCD265 will be performed using specific validated bioanalytical methods.

7.5.2 Pharmacodynamic Evaluation

Pharmacodynamic parameters that may be investigated in this study include but are not limited to plasma levels of hepatocyte growth factor (HGF) and shed-MET receptor, prior to and during treatment. At each PD time point, whole blood samples will be collected into 10-mL K2EDTA tubes. For PD analysis, a total of approximately 40 mL of blood will be collected from each patient.

7.5.3 Circulating Tumor DNA

Blood samples for ctDNA analysis will be collected at pre-screening or baseline, at the time of disease evaluation to confirm a disease response (PR or CR) and at the End of Treatment visit, as outlined in Table 2. For patients who are enrolled based on prospective ctDNA testing, an additional sample may be requested prior to dosing to ensure adequate amounts of blood have been received to complete the remainder of analyses required per protocol. Parameters that will be evaluated include but are not limited to *MET* mutations, *MET* gene amplification, *MET* gene rearrangement, and other genetic mutations or gene copy number changes associated with the pathogenesis of human cancers.

At each ctDNA time point, blood samples will be collected into two 10mL Streck brand Cell-Free DNA Blood Collection tubes allowing shipping and stability at ambient temperatures. For ctDNA analysis, the total volume of blood to be collected between pre-screening and End of Treatment will be up to approximately 60 mL of blood.

7.6 Post-treatment Follow-up

Post-treatment follow-up for survival will be conducted by telephone contact or other methods every 2 months (\pm 14 days) until death or lost to follow-up. Treatments received subsequent to study participation will be collected and recorded in the CRF.

8 ADVERSE EVENT REPORTING

8.1 Sponsor Medical Monitor Personnel

The contact information for the sponsor's Medical Monitor personnel for this trial is available in the study contact list located in the Study Manual.

8.2 Adverse Events

An adverse event (AE) is any reaction, side effect or other undesirable medical event that occurs during participation in a clinical trial, regardless of treatment group or suspected causal relationship to study treatment. All observed or volunteered AEs will be recorded in source documents and reported in the CRF. The best available medical terminology should be used to describe AEs in source documents and CRFs. Terms describing the diagnosis are preferred over individual signs and symptoms of the diagnosis. If determination of the diagnosis is delayed, record signs and symptoms and add the diagnosis as an additional AE when available; follow all recorded AEs to resolution. Examples of AEs include but are not limited to:

- Signs or symptoms of co-morbidity, illness, or toxicity of study treatment;
- Signs or symptoms of worsening malignancy under study (disease progression assessed by measurement of malignant lesions should not be reported as an AE).
- Laboratory abnormalities (see Section 8.2.1 for guidance for reporting in CRF);
- Hypersensitivity;
- Drug abuse, dependency, overdose, withdrawal or misuse;
- Signs or symptoms of drug interactions;
- Extravasation;
- Exposure during pregnancy or via breastfeeding;
- Medication error; or
- Occupational exposure.

8.2.1 Laboratory Abnormalities

An abnormal laboratory test results should be reported as an AE in the CRF only if it is associated with one or more of the following:

- Clinical symptoms;
- Requires additional tests (beyond repeats), treatment or intervention;
- Results in change in study treatment dosing;
- Requires discontinuation from study treatment; and/or
- Considered by the investigator or Sponsor to be an AE.

Hy's Law

Hepatic function abnormality defined by an increase in AST and/or ALT to $\geq 3 \times$ ULN concurrent with an increase in total bilirubin to $\geq 2 \times$ ULN but without increase in alkaline phosphatase (i.e., alkaline phosphatase $< 2 \times$ ULN) meets the criteria for Hy's Law and raises the concern for drug-induced liver injury when no other cause of the abnormal laboratory results is identified. Follow-up investigations and inquiries will be initiated promptly by the investigational site to determine whether the findings are reproducible and/or whether there is objective evidence that clearly supports causation by a disease (e.g., cholelithiasis and bile duct obstruction with distended gallbladder) or an agent other than the investigational product.

Cases meeting Hy's Law should be reported as SAEs. Study drug should be permanently discontinued for a Hy's Law case.

